5.1 General Considerations

Except where otherwise specified, the following general principles apply to the planned statistical analyses. All statistical analysis will be conducted using SAS version 9.4 or later (SAS Institute Inc., Cary, NC) or other widely-accepted statistical or graphical software as required.

5.1.1 Descriptive Statistics

Continuous data will be summarized with mean, standard deviation, median, minimum, maximum, and number of evaluable observations. Categorical variables will be summarized with frequency counts and percentages. Confidence intervals may be presented, where appropriate, using the t-distribution for continuous data and Clopper-Pearson Exact method for categorical variables.

5.1.2 Visit Windows

Unless otherwise specified, visit based assessments will be analyzed for each analysis time point according to the nominal visit entered in the Case Report Form (CRF) regardless of if it is out of window.

5.1.3 Statistical Significance

Unless otherwise specified, hypothesis testing will be performed at the two-sided 0.05 significance level. P-values will be rounded to three decimal places. If a p-value is less than 0.001 it will be reported as "<0.001". If a p-value is greater than 0.999, it will be reported as ">0.999".

5.2 Analysis Sets

The following analysis sets are defined for analysis:

- Modified Intent to Treat (mITT): All randomized subjects to the test arms who successfully complete the Trial Phase and all successfully randomized subjects to the control arm.
- Intent-to-Treat (ITT): All successfully randomized subjects who met all the enrollment criteria.
- Per-Protocol (PP): All test subjects who received a permanent device implant and all control subjects who contributed their data to the primary and secondary endpoint without any major protocol deviations (that would render their data unevaluable).

The primary analysis of the primary and secondary endpoints will be performed on the mITT population. Supportive analyses will be performed for the Intent-to-Treat and Per-Protocol population.

For secondary endpoint analyses incorporating crossover data (i.e. data gathered in the post 6-month periods), sensitivity analyses will be performed to examine the impact of crossover.

If a supportive analysis set is the same as the mITT set, the results will be the same and will not be regenerated for that supportive analysis set.

Statistical Analysis Plan		Page 8 of 14
Sponsor SGX International	Study EU RCT DTM SCS vs. CMM	Version 3.0

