Exclusion Criteria	
A subject must NOT MEET ANY of the following exclusion criteria:
 
 
1. Had previous lumbar spinal surgery (e.g., lumbar fusion, discectomy, laminectomy, laminotomy)
 
2. Has a medical, anatomical, and/or psychosocial condition that is contraindicated for commercially available Intellis™ SCS systems as determined by the Investigator
 
3. Has a diagnosed back condition with inflammatory causes of back pain (e.g., onset of severe pain with activity), serious spinal pathology and/or neurological disorders as determined by the investigator
 
4. Be concurrently participating in another clinical study
 
5. Has an existing active implanted device such as a pacemaker, another SCS unit, peripheral nerve stimulator, and/or drug delivery pump, etc.
 
6. Has a pain in other area(s) and/or medical condition requiring the regular use of significant pain medications that could interfere with accurate pain reporting, and/or confound evaluation of study endpoints, as determined by the Investigator
 
7. Has mechanical spine instability as determined by the Investigator
 
8. Has undergone, within 30 days prior to enrollment, an interventional procedure to treat back and/or leg pain, which is providing significant pain relief
 
9. Has unresolved major issues of secondary gain (e.g., social, financial, legal), as determined by the investigator
 

	
10. Be involved in an injury claim under current litigation or has a pending or approved worker's compensation claim
 
11. Be pregnant (determined by urine testing unless female subject is surgically sterile or post-menopausal. If female, sexually active, and childbearing age, subject must be willing to use a reliable form of birth control.)

Primary Endpoint	The primary efficacy endpoint is the percentage of randomized subjects who respond (a decrease in back pain VAS by at least 50% compared to baseline) to SCS therapy at 6 months (superiority analysis). Subjects who do not have a successful Trial Phase are considered failures (non-responders) toward the primary endpoint.
Secondary Endpoints & Additional Measures	Secondary endpoints of this study are to further document the safety, clinical effectiveness and health economic analytics of the DTM™ SCS delivered through IntelliS™ system when compared to CMM alone for the treatment of chronic pain of the back and limbs.

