### **B.6.6. Test Arm: End of Trial Assessment**

At the end of the Trial Phase, subjects will be assessed for pain intensity under optimal therapy parameters. Anterior-posterior (AP) and lateral X-ray imaging will be done at the end of the Trial Phase. The subject will be assessed for adverse events and medication usage.

Those who have a "successful Trial Phase" (defined as a 50% or greater pain reduction from Baseline in their back pain) will proceed to permanent implantation of the SCS system to evaluate DTM™ SCS therapy, and permanent implantation of the Intellis™ SCS system will be scheduled. A threshold of 50% for the Trial Phase was predetermined as the minimum pain reduction that warrants consideration of a permanent implant and an opportunity to achieve a 50% pain reduction as defined in the Individual Subject Success criterion (see Section B.7.3).

Data from subjects who did not achieve 50% or greater pain reduction in back pain will not receive permanent implantation and will be carried forward toward the primary endpoint. These subjects will have the leads explanted and will exit the study. Following this exit, subjects will be followed by the Investigator at regular intervals, as dictated by standard of care at each site, in order to facilitate pain management. Any additional non-study related monitoring of the subject will be the responsibility of the subject's personal physician, as dictated by reasonable medical care.

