## B.7. Study Endpoints

### B.7.1. Definition of Analysis Populations

- Modified Intent to Treat (mITT): All randomized subjects to the test arms who successfully complete the Trial Phase and all successfully randomized subjects to the control arm.
- Intent-to-Treat (ITT): All successfully randomized subjects who met all the enrollment criteria.
- Per-Protocol (PP): All test subjects who received a permanent device implant and all control subjects who contributed their data to the primary and secondary endpoint without any major protocol deviations (that would render their data unevaluable).

The primary analysis of the primary and secondary endpoints will be performed on the mITT population. Supportive analyses will be performed for the Intent-to-Treat and Per-Protocol population.

For secondary endpoint analyses incorporating crossover data (i.e. data gathered in the post 6-month periods), sensitivity analyses will be performed to examine the impact of crossover.

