### B.7.2. Effectiveness Assessment Definitions

- Primary Effectiveness Assessment: For test subjects who have a successful Trial Phase and receive a permanent implant, the Primary Efficacy Assessment occurs at the follow up visit 6 months after Device Activation. For subjects who do not have a successful Trial Phase (based on subject's pain score) or subjects who do not want a permanent device implant due to insufficient pain relief (based on subject's discontinuation reason), the Primary Efficacy Assessment occurs at the end of the Trial Phase. For control arm subjects, the Primary Efficacy Assessment occurs at the 6 months follow up visit post-randomization.

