5.3 Handling of Missing Data

Missing data will be minimized by rigorous follow-up and investigator and site training. Additionally, for subjects in the DTM™ SCS arm who do not have a successful Trial Phase, results from the Trial Phase will be utilized for the primary endpoint as described in Section **Error! Reference source not found..** Methods for handling missing data for primary and secondary endpoints are also described in 5.3 and 5.7.2.1. Additionally, sensitivity analyses for missing data will be performed. Unless otherwise specified, all other analyses will be based on the evaluable data with no imputation.

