5.7.1.1 Primary Analysis

The *primary efficacy endpoint* will be evaluated with a Pearson Chi-square binomial test for superiority at the two-sided 0.05 alpha level.

H_0 : The percentage of subjects (P) who achieve a 50% improvement in their back VAS pain score at 6 months in the Test group is the same as in the Control group.

$$P_{\text{Test}} = P_{\text{Control}}$$

H_1 : The percentage of subjects (P) who achieve a 50% improvement in their back VAS pain score at 6 months in the Test group is superior to that in the Control group.

$$P_{\text{Test}} \neq P_{\text{Control}}$$

Primary analysis will be based on the mITT analysis set.

In addition to the results from the hypothesis test, the numerator and denominator and percentage responders will be presented.

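### The primary set drops test-arm subjects who withdraw during the Trial Phase but keeps every control, and the mITT wording conflicts with the rule that Trial Phase failures count

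*SAP*

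**What the plan says.** Both documents name the mITT set as primary: "The primary analysis of the primary and secondary endpoints will be performed on the mITT population" (protocol B.7.1) and "Primary analysis will be based on the mITT analysis set" (SAP 5.7.1.1). Its definition is the same in both: "All randomized subjects to the test arms who successfully complete the Trial Phase and all successfully randomized subjects to the control arm". ITT and per-protocol analyses are supportive.

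The synopsis sets the endpoint over everyone randomized: "The primary efficacy endpoint is the percentage of randomized subjects who respond". It adds: "Subjects who do not have a successful Trial Phase are considered failures (non-responders) toward the primary endpoint". Protocol B.6.6 describes a successful Trial Phase as one "defined as a 50% or greater pain reduction from Baseline in their back pain". For subjects without a successful trial, judged on the pain score, or who decline an implant because relief was insufficient, protocol B.7.2 says that "the Primary Efficacy Assessment occurs at the end of the Trial Phase".

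SAP 5.7.1.2 sorts test subjects into three groups:
- Those who fail the Trial Phase keep their Trial Phase score at every time point.
- Those who withdraw before completing it (adverse event, non-compliance, withdrawn consent and similar) are left out of the mITT set.
- Those who complete it but lack a 6-month score are multiply imputed, as are controls with missing scores. Imputation is run separately by arm.

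SAP 5.7.2.1 repeats the removal for the secondary endpoints, on the ground that these subjects have no End of Trial score. The Definition of Success section of the protocol rests study success on the primary superiority test alone.

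**The concern.** The Trial Phase exists only in the test arm, so a rule tied to completing it can remove subjects from that arm only. A control who withdraws consent in the second week stays in the denominator and is imputed; a test subject who does the same during the Trial Phase disappears. The stated reasons include adverse events and non-compliance, which may well be related to outcome. If those who leave would mostly not have responded, removing them raises the test-arm rate with no treatment effect behind it. The trial is open-label and a single test decides success, so the denominator should be beyond argument before anyone looks at the data.

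The second problem is one of drafting. The mITT definition makes success a condition of membership, and success elsewhere means at least 50% back pain relief. A programmer working from SAP 5.2 alone would drop the Trial Phase failures that other sections count. SAP 5.3 should lead the reader to the failure rule, but its sentence ("results from the Trial Phase will be utilized for the primary endpoint as described in Section") ends in a broken cross-reference.

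**Working it through.** **The plan's own figures.** Inputs from SAP section 4: 60% against 30%, two-sided 0.05, Pearson chi-square, 50 per group.
- Power = Φ[(0.30·√50 − 1.96·√(2·0.45·0.55)) / √(0.60·0.40 + 0.30·0.70)] = Φ[(2.121 − 1.379)/0.671] = Φ(1.107) = 86.6%. Exact enumeration gives 87.6%. The stated figure of more than 85% is reproduced.
- 100/(1 − 0.33) = 149.3, or about 150 randomized and 75 per arm. This also agrees. The 33% combines Trial Phase non-completion with later exits and is not split, so it yields no Trial Phase withdrawal rate.

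**Who is in the test-arm denominator.**

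| Test-arm subject | SAP 5.2, read literally | SAP 5.7.1.2 and 5.7.2.1 |
|---|---|---|
| Withdraws during Trial Phase | out | out |
| Completes it, under 50% relief | out | in, with Trial Phase score |
| Completes it, at least 50% relief | in | in |

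Every randomized control is in under both columns. The first row does not depend on how 5.2 is read. The second row is the wording conflict.

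**Effect of removing withdrawals only.** Assumptions: 75 randomized per arm, true response 30% in both arms among all randomized, complete data otherwise, Pearson test with critical value 3.8415, and assumed withdrawal rates w of 2%, 5% and 10% (on average 75w = 1.5, 3.75 and 7.5 subjects). Rejection probabilities come from exact binomial enumeration, with a random number withdrawn.

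If every withdrawal is a non-responder, the test-arm rate in the analysed set becomes about 0.30/(1 − w):

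| w | Test-arm rate | Error favouring test | Two-sided error |
|---|---|---|---|
| 0 | 30.0% | 2.4% | 4.9% |
| 2% | 30.6% | 3.0% | 5.1% |
| 5% | 31.6% | 4.0% | 5.6% |
| 10% | 33.3% | 6.4% | 7.3% |

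If withdrawals have average prognosis, the test-arm rate stays at 30% and the two-sided error is 5.0%, 5.1% and 5.1%.

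The critical value should not be shortened to 3.841. The table with 28 against 17 responders of 75 has a chi-square of 3.8413, so the shorter value moves the no-withdrawal error to 5.2%.

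**Keeping withdrawals in as non-responders.** Under the null with average-prognosis withdrawals, the test-arm rate is 0.30·(1 − w). At 10% that is 27%: two-sided rejection is 6.8%, of which 0.9% favours the test arm.

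If the planned 60% was meant for Trial Phase completers, the rate among all randomized is 0.60·(1 − w), against 30% in controls:

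| w | Test-arm rate | Power, 75 per arm | Power, 60 per arm |
|---|---|---|---|
| 2% | 58.8% | 95.6% | 90.3% |
| 5% | 57.0% | 93.0% | 86.2% |
| 10% | 54.0% | 86.5% | 77.3% |

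The 60 per arm is an assumed information level after later exits; the documents give no such figure.

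**The case against.** A reader might infer from the definition that the primary analysis discards Trial Phase failures, with a large bias as the result. The documents do not support that. The synopsis, protocol B.6.6, B.7.2 and B.9.2.4, and SAP 5.3, 5.7.1.2 and 5.7.2.1 all carry failures into the endpoint. SAP 5.4 separates completing the Trial Phase from succeeding in it. The only test subjects whom SAP 5.7.1.2 expressly removes are those who withdrew before completing it. So the intended answer is clear, and what stands is a wording repair.

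On the withdrawals, the other side can say that the rule is pre-specified, that it is confined to exits before the End of Trial score, that later test-arm dropouts are imputed as controls are, and that a supportive ITT analysis, reasons for exclusion and missing-data sensitivity analyses are planned. All of that is true and limits the harm. It does not restore the randomized comparison in the test that decides success. Nor is the ITT safeguard complete: the imputation rule is written for mITT subjects, so the SAP does not say how Trial Phase withdrawals are scored in the ITT analysis.

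A reader might also infer that the synopsis already makes withdrawals non-responders. It does not settle this. Its sentence concerns subjects without a successful trial, and B.7.2 ties that to the pain score or to declining an implant for insufficient relief. Non-responder scoring also treats the arms differently, since control dropouts are imputed. It is a conservative choice among defensible ones.

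**Conclusion.** The point holds and should be fixed before analysis, though it does not undermine the trial. Test-arm Trial Phase withdrawals leave the primary set with no counterpart among controls, so the primary comparison is not between the groups as randomized and departs from the synopsis endpoint. The effect is small at low withdrawal and grows with the rate and with how strongly withdrawal selects non-responders. The rise in errors favouring the test arm, up to 6.4% at 10% withdrawal, needs every withdrawal to be a non-responder. The withdrawal rates, the 30% null rate, complete data and the plain Pearson test are assumptions. It would be wrong to infer that the error rate is known to be inflated: with average-prognosis withdrawals it is not materially changed. The stated power and sample size reproduce and are not in question here.

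**What to change.** - **Primary set** (protocol B.7.1, SAP 5.2 and 5.7.1): all randomized subjects, analysed as randomized. The present ITT definition adds an eligibility condition, so promoting it unchanged would not quite do this.
- **Trial Phase failures**: non-responders, as the synopsis and SAP 5.7.1.2 already imply.
- **Trial Phase withdrawals, responder endpoint**: keep them in under a rule fixed before analysis. One option is to score them as non-responders, with a sensitivity analysis that imputes them as missing control scores are imputed. The reverse order is also defensible. Keep multiple imputation for other missing 6-month scores.
- **Trial Phase withdrawals, mean VAS** (SAP 5.7.2.1): impute them. For both endpoints, state which arm's imputation model they are drawn from, since imputation is run by arm and these subjects lack the End of Trial score that the model uses.
- **mITT**: keep as supportive, reworded to cover test subjects who complete the Trial Phase with or without success.
- **Housekeeping**: repair the cross-reference in SAP 5.3, and state which subjects the planned 60% describes.

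The cost is wording in those sections and one sensitivity analysis, with no new patients or data. Under non-responder scoring the test-arm rate becomes less favourable. If 60% was meant for Trial Phase completers, power can fall below the planned 85% when withdrawal is near 10% and later exits also occur.

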3.2 Blinding

Due to the nature of the treatment groups, comparing an implantable medical device with conventional medical management that may involve multiple different treatments, it is not feasible to blind the subjects, implanting physicians or the clinical site personnel to the group assignments. The assessment of treatments are done by the subjects and not by the site personnel, so the lack of blinding of site personnel should not affect results as pain is the major assessment and subjects tend to describe pain truthfully since it affects their everyday life dramatically and not be influenced by knowledge of which treatment arm they are assigned to. In order to minimize potential assessment bias, the subjects will receive the standard instructions for completing the questionnaires.

4 Sample Size Determination

The clinical investigational plan requires a screening process for all subjects that provide written informed consent. These subjects will undergo screening to assess eligibility. Subjects may be excluded for various reasons during screening. Accordingly, in order to include an estimated 150 subjects to the point of randomization, up to 300 subjects may need to be consented and enrolled to account for exclusions prior to randomization.

The sample size estimate to determine primary endpoint is based on the primary objective of demonstrating superiority of the test group to the control group. Established methods were followed in determining the superiority criteria and the related sample size estimate

- Test basis: Pearson Chi-square binomial test for superiority
- Estimated responder rate of 60% in the test group and 30% in the control group
- Significance level, alpha, of 0.05 two-sided
- Randomization: 1:1

With these assumptions, a sample size of 50 subjects in each group will result in greater than 85% power for the study.

Based on the primary endpoint requirement, a minimum of 50 subjects per treatment group are required (100 total). To account for a combined estimated attrition of 33% for subjects that do not complete the Trial Phase, and subjects that exit study before the 6-month primary endpoint visit, approximately 150 subjects would need to be randomized.

To account for 50% attrition prior to randomization (including subject ineligibility after signing the informed consent and subject dropout), it is estimated that a total of up to 300 subjects would need to be enrolled in the study.

Statistical Analysis Plan		Page 7 of 14

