5.9 Safety Analyses

Safety will be assessed by characterizing adverse events at all study visits with descriptive statistics.

All Adverse Events assessed/determined to be study-related study will document seriousness, severity, treatment/intervention provided, relationship to the device/procedure, and resolution.

Adverse events (AE) will be reported for the mITT set. A sensitivity analysis of AEs based on the ITT set will also be performed. AEs will be tabulated with the number of events and subjects with event for each event type and overall. Rates will be reported as the number of subjects who experience at least one event during the analysis interval out of the total number of subjects with follow-up to the beginning of the analysis interval. Serious adverse events will also be tabulated. The rate of all AEs and SAEs reported in the study will be reported.

All AEs and SAEs will also be summarized by relatedness as described above. Adverse events leading to death or study discontinuation will be provided in listing format.

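### No defined analysis set contains all randomized subjects: the set called ITT drops those later found ineligible, and the adverse event tables inherit that gap

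*SAP*

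**What the plan says.** SAP 5.2 and Protocol B.7.1 give the same three sets.

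- **ITT:** "All successfully randomized subjects who met all the enrollment criteria". What makes a randomization successful is not defined. Neither document says who identifies ineligibility after randomization, when, or with what knowledge of arm and outcome.
- **mITT (primary):** test subjects who complete the Trial Phase successfully, plus all successfully randomized controls. The control side carries no eligibility condition.
- **Per-protocol:** "All test subjects who received a permanent device implant and all control subjects who contributed their data to the primary and secondary endpoint", followed by a clause excluding major deviations.

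The primary endpoint in the protocol synopsis is a proportion of those randomized, with trial failures counted as non-responders. SAP 5.7.1.2 carries the Trial Phase VAS of trial failures forward to every time point. It removes from mITT only those who withdrew before completing the Trial Phase, and SAP 5.7.2.1 gives the reason that they have no End of Trial score. Multiple imputation in SAP 5.7.1.2 is written for mITT subjects. Under SAP 5.3, analyses without their own rule use evaluable data and no imputation.

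In SAP 5.9 the adverse event tables use mITT, and "A sensitivity analysis of AEs based on the ITT set will also be performed". The same section also promises overall AE and SAE rates for the study and a listing of events that led to death or discontinuation.

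**The concern.** A set called intent-to-treat should keep the groups that randomization formed. This one adds a condition that may be assessed after assignment. Secondary gain, spinal instability, interfering pain and device contraindication are all left to the investigator (Protocol B.3.3), and the investigator knows the arm.

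The condition is worded alike for both arms but need not act alike. Candidacy for trial and implant is an inclusion criterion. Only test subjects then have pre-operative assessment (Protocol B.6.3), lead placement and, for some, a repeat pregnancy test (Protocol B.6.5). A problem that existed at entry is therefore more likely to come to light in the test arm.

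Two things are at stake. The supportive analysis that should follow the randomized comparison may be shifted by selection. And some test subjects exposed to the Trial Phase procedure may fall outside both sets on which adverse events are tabulated.

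**Working it through.** **1. The plan's own figures.** Inputs from SAP section 4: "Estimated responder rate of 60% in the test group and 30% in the control group"; "Significance level, alpha, of 0.05 two-sided"; "Randomization: 1:1"; and the statement that "a sample size of 50 subjects in each group will result in greater than 85% power for the study".

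Power = Φ[(|p1 − p2|·√n − 1.96·√(2·p̄·(1 − p̄))) / √(p1(1 − p1) + p2(1 − p2))]

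With n = 50 and p̄ = 0.45: (0.3 × 7.071 − 1.96 × 0.7036) / 0.6708 = (2.121 − 1.379) / 0.6708 = 1.107, so power is 86.6%. Exact enumeration of the Pearson chi-square gives 87.6%. The claim is reproduced.

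The inflation starts from a "combined estimated attrition of 33% for subjects that do not complete the Trial Phase" and for exits before 6 months: 100 / 0.67 = 149.3, stated as about 150, or 75 per arm. The sample size is not in dispute.

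**2. Who is in which set.**

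| Randomized subject | mITT | ITT |
|---|---|---|
| Test, failed Trial Phase, eligible | In under SAP 5.7.1.2; out if SAP 5.2 is read literally | In |
| Test, withdrew during Trial Phase, eligible | Out | In, but no outcome rule |
| Test, withdrew during Trial Phase, later found ineligible | Out | Out |
| Test, implanted, later found ineligible | In | Out |
| Control, later found ineligible | In | Out |

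The third row is in neither set. The last two rows show that ITT is narrower than mITT on eligibility. The second row has an outcome gap: the imputation covers mITT subjects only, so the subjects whom ITT adds have no stated handling of their missing result.

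**3. Effect of ITT exclusions on the responder rate.** The documents give no number of late-found ineligible subjects, so 5 is an assumption, as is removal from the test arm only and of non-responders only.

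- At a 60% rate: 45/75 = 60.0% becomes 45/70 = 64.3% (+4.3 points).
- At about 45%: 34/75 = 45.3% becomes 34/70 = 48.6% (+3.2 points).
- Per subject removed: 45/74 = 60.8% (+0.8) and 34/74 = 45.9% (+0.6).

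**4. Effect on false-positive risk.** Exact enumeration, 75 per arm, true rate 30% in both arms, chance that the two-sided chi-square favours the test arm:

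- Nobody excluded: 2.4%.
- 1, 2, 4 or 8 test non-responders excluded, no controls: 2.9%, 3.2%, 4.4%, 6.2%.
- Equal numbers excluded from both arms, unrelated to outcome (1 to 8 per arm): 2.5% to 2.6%. Power at 60% versus 30% falls from 96.8% to 94.1% with 8 per arm excluded.

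**5. Per-protocol set.** Implant requires at least 50% relief in the Trial Phase (Protocol B.6.6), and the control arm has no matching filter. Assume a true rate of 30% in both arms as randomized (22.5 expected responders of 75), a share q of the test arm not implanted, all of these non-responders, and all 75 controls kept. The documents do not give q.

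| q | Test n | Test rate | Chance of favouring test |
|---|---|---|---|
| 5% | 71 | 22.5/71 = 31.7% | 4.4% |
| 10% | 68 | 22.5/68 = 33.1% | 6.2% |
| 20% | 60 | 22.5/60 = 37.5% | 15.5% |
| 33% | 50 | 22.5/50 = 45.0% | 40.8% |

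The last row takes the whole planned attrition as non-implantation. That is an upper end, since the 33% also covers later exits.

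**The case against.** The best defence is that late ineligibility should be rare. Protocol B.6.2 confirms eligibility before baseline, randomization follows, and key criteria are fixed at enrollment. No text provides for re-judging eligibility once the outcome is known, and the condition is nominally the same in both arms. SAP 5.4 will report the size of each set with reasons for exclusion. All of this stands, and it is why the ITT effect is called small. It does not close the gap, because reporting exclusions is not an analysis of everyone randomized.

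A reader might infer that mITT conditions on trial success, so that all three sets are selected and the supportive analyses show nothing. The documents do not support that. The wording of SAP 5.2 allows it, but SAP 5.7.1.2, SAP 5.7.2.1 and the synopsis indicate that trial failures stay in as non-responders, and SAP 5.4 distinguishes completing the Trial Phase from succeeding in it. ITT also brings back eligible Trial Phase withdrawers, so it still addresses selection in mITT.

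A reader might also infer that some device-arm harms vanish from the report. SAP 5.9 contradicts this: the overall event rates and the listing of events leading to discontinuation are not tied to an analysis set. The fair statement is that such a subject is in neither set named for the adverse event tables.

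On per-protocol, the deviation clause can be read as covering both arms, and such sets condition on treatment received by design. Both points are fair. Selection on early response in the test arm remains on either reading.

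**Conclusion.** The point holds as a defect of definition with a cheap remedy. It is not evidence that the primary result is biased. No defined set contains all randomized subjects, and ITT carries an eligibility condition that mITT does not place on controls.

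The likely effect of the ITT wording is small. Reaching 3 to 4 points on the test responder rate takes five exclusions, all non-responders and all from the test arm, which is an assumption and a worst case. Exclusions balanced between arms and unrelated to outcome leave the false-positive risk essentially unchanged.

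The per-protocol set is the more strongly selected of the two supportive sets. How strongly depends on the unknown share not implanted and on the assumption that none of those subjects would have responded. Agreement between it and the primary analysis should not be read as confirmation free of selection.

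For safety, the main tables omit test subjects who withdraw during the Trial Phase because of an adverse event, and the sensitivity analysis restores only those who met every criterion.

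**What to change.** 1. In SAP 5.2 and Protocol B.7.1, define ITT as all randomized subjects, analysed in the arm assigned, and delete the eligibility condition.
2. Extend the missing-data rule in SAP 5.7.1.2 to this set. Use one rule for both arms that covers test subjects with no End of Trial score, and add a sensitivity analysis that counts every missing outcome as non-response. Without this step the new ITT analysis would be undefined for the subjects it adds.
3. In SAP 5.9, run the main adverse event tables on all randomized subjects.
4. Apply the per-protocol data-availability and major-deviation conditions to both arms, with membership decided before database lock. State that the test side of this set remains selected on Trial Phase response. A common rule that still requires the assigned treatment does not remove that selection, because the implant itself depends on it.

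The cost is wording in a few sections and a little more analysis, with no new data. ITT estimates may be slightly diluted by a few ineligible subjects. Power is not a constraint: with all 75 per arm counted at 60% versus 30%, the formula in the working gives (0.3 × 8.660 − 1.379) / 0.6708 = 1.817, or 96.5% (exact 96.8%), provided every subject has an outcome or is counted by a stated rule.
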